6.6 Potential Toxicity Management

All preclinical evidence indicates that systemic exposure of P-321 via ocular topical administration is none or negligible at concentrations up to 10-fold higher than the concentration planned in this study (the estimated systemic safety margins for the doses anticipated in this study range from 75- to 375-fold). However, since P-321 is an ENaC inhibitor, a previous potential safety signal of concern following the administration of P-321, was drug-induced hyperkalemia. This possibility was carefully investigated in Study P-321-101. No changes in plasma or serum potassium were noted in this study in subjects administered 0.01% P-321 Ophthalmic Solution BID for up to 28 days.

No concerns for systemic toxicity in this single-dose administration study are based on the lack of safety findings from the P-321-101 study when treatment with P-321 was administered BID for up to 28 days. In addition, in the same study, the pharmacokinetic results demonstrated a lack of systemic availability of 0.01% P-321 Ophthalmic Solution given twice daily for 28 days. In this study, treatment with P-321 Ophthalmic Solution at doses up to 0.05% will be given only **once** to each participating subject. Thus, no post dose monitoring of serum potassium is planned for this trial.

Any additional questions regarding toxicity management should be managed by appropriate medical professional at the clinical site and directed to Parion Sciences Medical Monitor.

6.7 Collection of Data

Source documentation for data collected in the study will be maintained at the investigative site. In cases where no source documents will be used (i.e., data will be recorded directly onto the CRF without first being recorded on another document, such as the subject symptom questionnaires, for which data will be recorded directly on the CRF pages by the subject), the original data will be included in the CRF and this will be noted in the investigator files.

7 TREATMENT OF SUBJECTS

7.1 Treatment Administration

Study medication will be administered by the PI or clinical site personnel at Visits 2 and 3. At Visit 2, eligible subjects will be randomized (1:1 ratio) to receive one of two treatment sequences: P-321 Ophthalmic Solution at Visit 2, and Placebo at Visit 3, or Placebo at Visit 2 and P-321 at Visit 3. The order of the treatment is randomized, neither the subjects nor site personnel will know which treatment the subject receives at which visit. Assessments will be conducted before and at the indicated times after study medication administration in the indicated order in [Section 6](#).

7.2 Trial Treatments

Subjects will receive P-321 Ophthalmic Solution or Placebo in random order at Visit 2 and 3. The study treatment order will be determined by the assignment of the randomization code. P-321 Ophthalmic Solution and Placebo.

P-321 Ophthalmic Solution is a sterile, aqueous, non-preserved solution of approximately pH 5, and tonicity of approximately 290 mOsm/kg. Placebo solution has identical composition without the active ingredient. Both solutions are packaged in low density, polyethylene dropper bottles. Each bottle of study medication will contain sufficient volume of ophthalmic solution for the intended dosing (1 drop in each eye). Only one drop should be instilled in each eye.

For Phase 1, one pouch of study medication will be used at each clinical visit, the label on the pouch will indicate the visit number at which the drug will be administered (Visit 2 or Visit 3). The labels on the kit and the pouches will minimally contain the following information: Study ID, kit number, storage temperature, and “Caution: New Drug – Limited by Federal Law to Investigational use”. The study medications will be stored at approximately 2-8°C in a secure area with limited access to study personnel.

For Phase 2, the dose selected of P-321 Ophthalmic Solution and Placebo will be provided by a compounding pharmacy in individual vials similar to those of the Phase 1 study, based on a randomization code. No medication kits will be prepared for Phase 2. The pharmacy will be unmasked to distribute according to the randomization scheme. The study medications will be stored at approximately 2-8°C in a secure area with limited access to study personnel and should be labeled and “Caution: New Drug – Limited by Federal Law to Investigational use”. Pharmacy records should include Study ID, randomization number, visit number, date, and subject identifiers.

The medication will be administered by the PI or clinical site personnel at each of Visit 2 and Visit 3. There will be no study medication administered at an Early Termination Visit.

7.3 Methods to Minimize Bias

To minimize bias, the treatment regimen will be randomized and masked. The randomization code will be generated by an independent designee of Parion Sciences, Inc. who is not involved in the day-to-day conduct of the clinical study. The randomization code will be provided to the designee of Parion Sciences, Inc. who is responsible for the manufacture, packaging and labeling

of the clinical supplies; further the randomization code will be maintained in a secure location separate from the clinical study site personnel.

The Medical Monitor and Principal Investigator and members of the Parion team not involved in the conduct of the study will be unmasked as part of the Data Review Group for decision making on the strength of P-321 Ophthalmic Solution to be used in Phase 2 of the study. The treatment assignments will remain masked to subjects in the study, the clinical monitor, and other site and Parion Sciences personnel involved in the conduct of the study and not involved in the Data Review Group. Additional unmasked reviews of subject data may occur throughout the study to make recommendations on further dose adjustments and for planning purposes. These reviews will follow the procedures outlined in [Section 6.5](#).

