6.4 Early Termination Visit

The following assessments will be performed at the Early Termination Visit for randomized subjects who are withdrawn from the study prematurely:

- Assess adverse events since the last visit and during this visit
- Assess concomitant medications and medical changes since last visit
- Collect vital signs (pulse, blood pressure, temperature and respiration rate) and height and weight
- Conduct an abbreviated physical examination (including respiratory, cardiovascular, musculoskeletal, gastrointestinal, and dermatological)
- Conduct a biomicroscopy and external eye examination

6.5 Selecting Dosage Strength in Phase 2

The decision of dose strength for P-321 Ophthalmic Solution in Phase 2 of the study will be the responsibility of the Data Review Group constituted by the Principal Investigator (or a designee not directly involved in the conduct of the study), the Medical Monitor and representatives of Parion Sciences. Decision on the dose level to be given in Phase 2 will be made based on unmasked review of the study data from the first 8 subjects by the review committee. Data to be considered will include safety and efficacy measures. A detailed criterion for Dose selection for Phase 2 is described in [Appendix XIV](#) and outlined below.

The dose level may be increased to 0.05% in Phase 2 in the event that:

- 1) No cases of serious, suspected related, unexpected events are noted in Phase 1 OR
- 2) No cases of serious ocular safety events are noted in Phase 1
- 3) Lack of evidence that P-321 produced an increase in tear volume based on OCT and/or Keratograph 5M, or evidence that additional improvements in tear volume (or the duration of effect) may be obtained with a higher dose.

The dose level may be decreased to 0.01% in Phase 2 in the event that:

- 1) No cases of serious, suspected related, unexpected events are noted in Phase 1
- 2) No cases of serious ocular safety events are noted in Phase 1
- 3) There is evidence of a significant increase in tear volume and the duration of effect based on OCT and/or Keratograph 5M

The dose level may remain at 0.017% (the same as in Phase 1) in the event:

- 1) No cases of serious, suspected related, unexpected events are noted in Phase 1
- 2) No cases of serious ocular safety events are noted in Phase 1
- 3) There is not compelling data to either increase or decrease the strength for Phase 2.

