The Data Review Group will make a recommendation to Parion Sciences to increase the dose, decrease the dose or maintain the dose.

Additional unmasked reviews of subject data may occur throughout the study to make recommendations on further dose adjustments and for planning purposes. These reviews will follow the procedures outlined above.

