7.7 Maintenance of Randomization and Procedure for Breaking the Code

The treatment assignments will be masked to the investigator, medical monitor, study site personnel, subjects in the study and those involved in the conduct of the study.

Only in the case of a medical emergency, or occurrence of a suspected related, unexpected, SAE, may the randomization code be unmasked and made available to the investigator, medical monitor, subject, and/or other personnel involved in the monitoring or conduct of this study. In the absence of medical need, the randomization code will not be available to the above personnel until after the study is completed and the database is locked.

The Data Review Group will review unmasked data. The Medical Monitor and Principal Investigator (or designee) and members of the Parion team not involved in the conduct of the study will be unmasked as part of the Data Review Group for decision making on the strength of P-321 Ophthalmic Solution to be used in Phase 2 of the study. The treatment assignments will remain masked to subjects in the study, the clinical monitor, and other site and Parion Sciences personnel involved in the conduct of the study and not involved in the Data Review Group. Additional unmasked reviews of subject data may occur throughout the study to make recommendations on further dose adjustments and for planning purposes. These reviews will follow the procedures outlined in [Section 6.5](#).

For Phase 1, a randomization list will be generated and the kits will be labeled in a masked fashion. The randomization assignments will be kept in a secure area at Parion Sciences, Inc. or designee. For Phase 2, a randomization list will be provided to the pharmacy and the pharmacy will distribute the assigned drug according to the randomization schedule with subjects remaining masked.

In case of a medical need, the investigator will treat the subject as needed regardless of randomized treatment. Since there is no specific antidote to P-321 Ophthalmic Solution, immediate emergency unmasking is not necessary. If the investigator feels it is necessary to unmask a subject's treatment assignment after an emergency situation, the investigator must call the medical monitor and notify Parion Sciences, Inc. The treatment assignment will be revealed on a subject-by-subject basis, leaving the masking of the remaining subjects intact.

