All meniscus variables of upper (**A**) and lower (**B**) tear menisci are measured with a custom software program with operator inputs (TDanalyer, ver. 1.0) ([Figure 2](#)). Touch points (*pink dots*) between two elements (eyelid, cornea, and tear meniscus) and a middle point (*green dot*) of the front edge of the tear meniscus are marked. After that, the software process the image, to yield the results. The three-point method is used to fit a circle to yield tear the meniscus height and area. Tear meniscus height and area of both upper and lower tear menisci will be used. In addition, the eye lid length will be photographed and measured to calculate tear meniscus volumes in both upper and lower tear menisci.

Figure 2: Measuring menisci variables with UHR-OCT

[figure not shown]

Tear Meniscus Height measured by Keratograph 5M

[figure not shown]
Evaluation of tear film volume will be assessed via tear meniscus height measurements using the Keratograph 5M. High resolution images of the lower tear meniscus from both eyes are obtained under infrared light as indicated in the Keratograph 5M user manual. Using integrated magnification and measurement tools, the tear meniscus height of the lower lid margin are estimated. Detailed description of the operation of the instrument and software is described in Keratograph 5M user manual provided by Oculus.

Instructions:

[figure not shown]
- Turn on the computer. After turning on the computer the operating system loads the Keratograph 5M program. If necessary click on the Keratograph 5M icon .
- Turn on the Keratograph 5M
- Enter Subject information in the Patient Data Management Page.

[figure not shown]
- In the "Patient" box on the top left, select [New]. The following screen will appear:

- Enter the patient's last name, first name, and date of birth and click [Save].
- Click [Keratograph] in the “Functions” box to transition from the Patient Data Management to the Keratograph Overview.
- In the “Examination” menu click [New] and the following screen will appear:

- Activate the **[Tear Meniscus Height]** function button on the “TF Scan” Box on the left.
- In the illumination box on the right-hand side of the screen, select **[IR]** lighting.
- If necessary, adjust the camera for optimal focusing on the tear meniscus as seen on the example in the image below (i.e. at approximately the 6:00 position).

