APPENDIX XIV: DOSE SELECTION FOR PHASE 2 AND DATA REVIEW DURING STUDY

The decision on dosage strength to be used in Phase 2 will be the responsibility of the Data Review Group constituted by the Principal Investigator (or designee), Medical Monitor and representative(s) of Parion Sciences not involved in the conduct of the study. The Data Review Group may request the participation of an independent statistician to assist in the assessment of the safety of the study medication and the dosage strength selection for Phase 2.

The Data Review Group will review unmasked data in order to make a decision on the dose to be administered in Phase 2. The Data Review Group will convene when approximately 8 subjects have completed the study, or earlier if needed. The trial will continue enrolling during the time the review by the Data Review Group is being prepared and being held. The Data Review Group will review the following to assist in making their recommendation for dose selection in Phase 2:

- Adverse events
- Biomicroscopy and external eye examination
- Drop instillation comfort assessments
- Abnormal alert laboratory results
- Tear volume via OCT
- Tear volume via Keratograph 5M

Recommendations by the Data Review Group may include:

- 1) The dose level may be increased to 0.05% in Phase 2 in the event that:
 - a) No cases of serious, suspected related, unexpected events are noted in Phase 1 AND
 - b) No cases of serious ocular safety events are noted in Phase 1
 - c) Lack of evidence that P-321 produced an increase in tear volume based on OCT and/or Keratograph 5M, or evidence that additional improvements in tear volume (or the duration of effect) may be obtained with a higher dose
- 2) The dose level may be decreased to 0.01% in Phase 2 in the event that:
 - a) There is evidence of a significant increase in tear volume and duration of effect in Phase 1 based on OCT and/or Keratograph 5M
 - b) No cases of serious, suspected related, unexpected events are noted in Phase 1
 - c) No cases of serious ocular safety events are noted in Phase 1
- 3) The dose level may remain at 0.017% (the same as in Phase 1) in the event that:
 - a) There is no compelling data to either increase or decrease the strength for Phase 2.
 - b) No cases of serious, suspected related, unexpected events are noted in Phase 1
 - c) No cases of serious ocular safety events are noted in Phase 1
- 4) Discontinue the study.
- 5) Amend the protocol

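### The protocol masks the investigator and medical monitor until database lock but also unmasks them on the Data Review Group, so bias in the operator-read primary measurement is not excluded

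*Combined protocol and SAP*

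**What the plan says.** All references are to the current protocol text, not the Version 1.0 text that follows it in the same file.

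**Masking rules.** Section 7.1 says that "neither the subjects nor site personnel will know which treatment the subject receives at which visit". Section 7.7 opens by masking the investigator, the medical monitor and site personnel. It permits the code to be broken only for a medical emergency or a suspected related, unexpected SAE. Without medical need, "the randomization code will not be available to the above personnel until after the study is completed and the database is locked".

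**Unmasking rules.** Section 7.3 says: "The Medical Monitor and Principal Investigator and members of the Parion team not involved in the conduct of the study will be unmasked". They are unmasked because they sit on the Data Review Group. Section 2.6 also names the Principal Investigator and offers no substitute. Section 6.5 describes a body "constituted by the Principal Investigator (or a designee not directly involved in the conduct of the study"); sponsor representatives and the Medical Monitor also belong to it. A later paragraph of 7.7, Section 8.1.5 and Appendix XIV also allow a designee but do not say that this person must be uninvolved.

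**Timing.** Appendix XIV convenes the group when about 8 subjects have completed, or earlier if needed, and adds: "The trial will continue enrolling during the time the review by the Data Review Group is being prepared and being held". Section 6.5 says: "Additional unmasked reviews of subject data may occur throughout the study".

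**Dosing and measurement.** Section 7.1 says: "Study medication will be administered by the PI or clinical site personnel at Visits 2 and 3". The trial has one centre. Under Appendix X the meniscus variables are "measured with a custom software program with operator inputs", and a second or third image replaces the first when the first is judged not good.

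**The concern.** The masking statements and the unmasking statements cannot all be followed. A site reading 7.1 and the opening of 7.7 would keep its Principal Investigator masked to the end. A site reading 2.6 and 7.3 would unmask that person partway through and let him or her go on dosing.

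This matters because the primary endpoint (Section 4.2.1) is a UHR-OCT measurement with two points of human judgement: where the meniscus points are marked, and which image is used. Appendix X gives no quality criterion for rejecting an image and names no masked reader. The investigator also verifies CRF entries (13.4), may withdraw subjects at discretion, with replacement (5.5), and rechecks at Visit 3 eligibility criteria that depend on the Principal Investigator's opinion (5.2, 5.3, 6.3). Someone who knows a subject's treatment could influence any of these, and the placebo comparison relies on masking to prevent that.

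**Working it through.** The point rests on no planned figure, so the check is mainly a comparison of passages.

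1. **Is the conflict real?** The opening of 7.7 names the investigator and the medical monitor as masked, and its exceptions are limited to medical need. Sections 2.6 and 7.3, and a later paragraph of 7.7 itself, unmask the same roles for dose selection, which is not a medical need. Section 7.1 has no exception at all. The conflict is real.

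2. **Does the designee wording remove it?**
 - 2.6 and 7.3: Principal Investigator, no designee.
 - 7.7, 8.1.5 and Appendix XIV: designee optional, involvement not addressed.
 - 6.5: designee optional, but must not be directly involved in conduct.

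 The designee is mandatory nowhere, so the wording does not remove the conflict. It also does nothing for the Medical Monitor.

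3. **Whose treatment can be disclosed before measurement is finished?**
 - The planned review of about 8 Phase 1 completers covers people whose measurements are over. It does not reveal the sequences of subjects randomised later.
 - An earlier-than-planned review, or an additional one, is not restricted to completers. Visits 2 and 3 are 7 to 14 days apart, so a subject can be under review with one treatment given and one outstanding.
 - There are only two sequences, AB and BA. If Visit 2 was A, Visit 3 must be B, and the reverse.
 - For such a subject, the UHR-OCT assessments still to come are 7 time points (1 pre-dose + 6 post-dose) x 2 eyes = 14. This is conditional on the subject being reviewed between visits, which no passage says will happen.

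4. **Can the person who knows affect the reading?** No passage says who operates the UHR-OCT software, and none bars an unmasked person from dosing, imaging or marking.

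5. **How sensitive would the test be?** The documents give no bias size, so this is an illustration on assumed values. Assume no true effect, N = 24, two-sided 0.05 (Section 8.3 does not state sidedness) and an average differential reading bias b across all subjects. P(reject) comes from a noncentral t with 22 df and noncentrality b/SE. Section 8.2 gives an SD of 71 µm. Both readings of it are shown:
 - 71 as the SD of the paired difference: SE = 71/√24 = 14.49 µm. For b = 5, 10, 20, 30 µm, noncentrality is 0.35, 0.69, 1.38, 2.07, and P(reject) is 6%, 10%, 26%, 51%.
 - 71 as the within-period SD: SE = 71 x √(2/24) = 20.50 µm. For the same b, P(reject) is 6%, 8%, 15%, 29%.

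 If only k of 24 subjects were exposed, the average bias would shrink to b x k/24. For example, 20 µm in 3 subjects averages 20 x 3/24 = 2.5 µm.

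**The case against.** The strongest reply is that 7.7 states a general rule and then its own exception, poorly joined, and that the sponsor can avoid the problem by using the designee. Additional reviews follow the Section 6.5 procedures, so its uninvolved-designee wording reaches them as well. Other site personnel outside the group stay masked. This stands as far as it goes: the plan permits a clean arrangement. It does not require one, and 2.6 and 7.3 do not mention one.

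It can also be argued that the phrase in 7.3 about not being involved in conduct covers the Principal Investigator. That is hard to sustain at a single site where the same person may instil the drops, and 6.5 attaches the phrase to the designee.

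Three further points stand in full. Instilling a drop is not measuring. No passage says the Principal Investigator acquires, selects or marks images. Safety data are not formally tested (8.1.4).

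A reader might infer that every Phase 2 image is exposed once the first review has taken place. The documents do not support that. Unmasking Phase 1 completers says nothing about Phase 2 sequences, and continued enrolment does not by itself unmask anyone.

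**Conclusion.** The masking sections contradict one another and should be corrected. As written, the plan does not exclude that a person who knows a subject's treatment doses that subject or handles the images behind the primary endpoint. The main route is an early or additional review that includes subjects between Visits 2 and 3. For those subjects the remaining treatment would be known with certainty.

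A reader might go further and conclude that the primary result is biased. The documents do not show this: the image operator is not named, and no passage says that subjects between visits will be reviewed. The size of any bias cannot be derived. The rejection rates above show only how the test would respond to assumed biases of 5 to 30 µm averaged over all 24 subjects.

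**What to change.** 1. In Sections 2.6 and 7.3, which name the Principal Investigator with no alternative, and in 6.5, 7.7, 8.1.5 and Appendix XIV, where the designee is optional, require a designee who is not directly involved in the study's conduct in place of the Principal Investigator. The current synopsis as supplied shows no Data Review Group wording. If the full synopsis has it, align it too.
2. Limit unmasked reviews for dose selection and planning to subjects who have completed both treatment visits or have withdrawn. Make an explicit exception for safety reviews, because Appendix XIV guarantees the group additional unmasked data when subject safety requires it. A limit to completers alone would conflict with that guarantee and would omit anyone withdrawn after Visit 2.
3. State that anyone who doses subjects, or who acquires, selects or marks OCT or Keratograph images, stays masked until lock, apart from the medical-need provision already in 7.7.
4. Write the Data Review Group exception into 7.1 and the opening of 7.7, and say plainly whether the Medical Monitor is masked or unmasked.

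The cost is small. Section 6.5 already provides for the designee, and dose selection still uses unmasked data. The Principal Investigator gives up a direct vote on the Phase 2 strength, and planning reviews may have to wait for subjects to finish Visit 3.
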